6.1 Study design

This will be a proof-of-concept randomized controlled trial (RCT) using mobile text messaging to optimize glycemic control in adults with type 2 diabetes.

6.2 Participants

6.2.1 *Setting of the study*

This study will be conducted in Nakuru County, located 157km North-West of Nairobi, Kenya (Appendix 1). Nakuru County covers an area of 7,495 km² and has 11 administrative Sub-Counties including Nakuru Town East, Nakuru Town West, Naivasha, Molo, Gilgil, Njoro, Kuresoi North, Kuresoi South, Rongai, Nakuru North and Subukia (98). The county is estimated to have a population of nearly 2 million people (99) and an estimated prevalence of 2.4% of type 2 diabetes among adults aged ≥50 years (6).

6.2.2 *Inclusion and exclusion Criteria*

Participants will be eligible for inclusion into the study if they meet the following criteria:

- a. adults over the age of 18 years;
- b. diagnosed the type 2 diabetes within the previous 1 year and obtaining care at a participating level 4 hospital;
- c. able to read English or Swahili Language (self-reported).
- d. currently own and able to read and send mobile text messages using any phone;

Participants will be excluded if they:

- a) are on dialysis;
- b) are pregnant;

- c) are unable to use mobile phone because of mental or visual impairment or any other reason.

6.3 Sample size

Hypothesis testing was not the objective of this study. However, for an effect size of 0.60, at a power of 0.80 and at an alpha level of 0.05, a sample size of 25 in each group has been used to results in a 1% reduction of HbA1c levels at post-test compared with pre-test (100). We therefore determined a sample size of 60 a-priori (n=30 intervention, n=30 control arm) to assess feasibility of text messaging in optimizing glycemic control. It is anticipated that this proof-of-concept study will obtain parameters that will be used in determining a robust power calculation for a fully powered efficacy trial, as it has been applied elsewhere in Bucci *et al.* (101).

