3.5 Research Objectives

The objective of this study is to evaluate the efficacy of a diet-related mHealth intervention on glycated hemoglobin among adults with type 2 diabetes.

By using one-way and interactive mobile telephone messages, this intervention seeks to achieve the following specific objectives:

1. Reduce glycated hemoglobin by at least 0.3% after 12 weeks
2. Increase food literacy scores as measured by the self-perceived food literacy scale

4 Conceptual Framework and Operationalization

The theoretical framework (Figure 2) of dietary behavior and food literacy is founded on the four components of food literacy in Vidgen *et al.* (77) and the attributes of food literacy described by Perry *et al.*, (79). The four components of food literacy include planning, selection, preparation and eating, while the attributes are skills, knowledge, and self-efficacy. Vidgen definition. (77) has been criticized for its emphasis on knowledge and excludes functional skills (96). Our operational definition therefore amalgamates a wider scope of definition of food literacy. Based on findings from our qualitative study conducted in the same population, it was found that two components of food literacy presented as the highest-ranking barriers to health dietary intake. We therefore developed the conceptual framework based on selection and eating of healthy dietary diet. BCW is applied to systematically identify the theoretical domains framework, intervention functions and behavior change techniques that were used to develop text messages for the intervention. It is anticipated that the text messages will influence changes selection and eating of healthy diets that will result in a reduction in HbA1C.

[figure not shown]

Figure 2. Conceptual Framework for dietary behavior outcomes and food literacy concepts

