4.1 Operational definition of independent and dependent variables

4.1.1 Definition of independent variables

- i. Food literacy: the interrelated combination of knowledge, skills and self-efficacy on food planning, selecting foods, food preparation, eating and evaluating information about food with the ultimate goal of developing a lifelong healthy, sustainable and gastronomic relationship with food (80).
- ii. Attribute of food literacy: quality or feature considered as a characteristic or integral part of food literacy (79,97)
- iii. Psychological capability: The mental capacity, knowledge or psychological skill to engage in the necessary thought (85)

- iv. Physical capability: The capacity, physical skill, strength, or stamina to perform an activity (85)
- v. Physical opportunity: The opportunity offered by the environment (85)
- vi. Social Opportunity: The cultural milieu, social cues and interpersonal influences that direct the way we think about things (85)
- vii. Reflective Motivation: Processes such as evaluating and planning (85)
- viii. Automatic motivation: The emotions, reactions, desires and impulses arising from associative learning and/or innate dispositions (85)

4.1.2 *Definition of dependent variables*

Glycated hemoglobin (HbA1c) is the average plasma glucose over the previous eight to twelve weeks (61).

5 Hypotheses/research questions

We hypothesize that using mHealth influences food literacy and dietary behavior hence reducing HbA1c by at least 0.3% in 12 weeks among adults with type 2 diabetes.

6 Study design and sampling strategy

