8.2 Plan for analysis of quantitative data

Quantitative data will be analyzed by the intention to treat principle (115). Various patient characteristics and primary outcome measures, including anthropometric and biochemical measurements (HbA1c, FBG, lipid profiles) at baseline will be summarized using descriptive statistics. The descriptive statistics will include means and standard deviations for continuous variables and proportions for categorical variables.

HbA1c levels will be compared at 3-months between the two arms using an ANCOVA which will control for baseline HbA1c levels. The intervention and the control groups will be followed-up for six months. One-way and interactive text messaging data will be analyzed descriptively.

A subgroup analyses per hospital and participant socio-demographics including age, sex, education, and income levels will be conducted. All statistical analyses will be performed using R version 4.0.3 (116).

9 Plan for communicating findings of the study

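### Section 6.3 derives 30 per arm from a pre-post power figure for a 1% HbA1c fall, which is not the power of the between-arm ANCOVA in 8.2 and does not relate to the 0.3% target

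*Protocol*

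**What the plan says.** Section 6.3 opens with a disclaimer: "Hypothesis testing was not the objective of this study". It then cites "effect size of 0.60, at a power of 0.80 and at an alpha level of 0.05, a sample size of 25 in each group" in connection with a "1% reduction of HbA1c levels at post-test compared with pre-test", and goes on: "We therefore determined a sample size of 60 a-priori (n=30 intervention, n=30 control arm"), the purpose being "to assess feasibility of text messaging in optimizing glycemic control". The section closes by saying that the study will supply parameters for the power calculation of a later, adequately powered trial. Section 9.4 calls the study a pilot, and 9.5 concedes that the sample size limits it.

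Other sections have a different aim. Section 3.5 sets an efficacy objective, and its first specific objective is "Reduce glycated hemoglobin by at least 0.3% after 12 weeks". Section 5 repeats this as a hypothesis: "reducing HbA1c by at least 0.3% in 12 weeks among adults with type 2 diabetes". Section 8.2 fixes the primary analysis: "HbA1c levels will be compared at 3-months between the two arms using an ANCOVA which will control for baseline HbA1c levels".

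No SD, baseline correlation, sidedness or dropout rate is given for the sample size, and neither 3.5 nor 5 says against what the 0.3% is measured.

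**The concern.** The one power figure in the protocol differs from the planned trial in two ways. Its contrast is post-test against pre-test, whereas 8.2 compares two arms. Its effect is 1%, more than three times the 0.3% in the objective and hypothesis. The word *therefore* nevertheless carries it over to the 30 per arm.

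A reader could attach the 0.80 to the primary comparison and then take a non-significant ANCOVA as evidence against the 0.3% target, which a trial of this size could not provide.

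**Working it through.** **Inputs from the protocol.** Effect size 0.60, power 0.80, alpha 0.05, 25 per group, a 1% fall, 30 per arm (6.3); a 0.3% target (3.5 and 5); between-arm ANCOVA adjusted for baseline (8.2).

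**Assumptions.** Two-sided tests unless noted, no dropout, and baseline correlation r varied. Power is from the noncentral t distribution.

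**1. Reproducing the 25.** Paired test, noncentrality 0.60·√n, df n−1: power is 0.785 at n=23, 0.804 at 24 and 0.821 at 25. So 24 are needed, and the stated 25 fits a within-group pre-post comparison. A two-arm unadjusted test with 0.60 taken as the between-arm standardised difference (noncentrality 0.60·√(n/2), df 2n−2) needs 45 per arm and has power 0.547 at 25. The figure therefore matches the pre-post wording and not a simple two-arm test.

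**2. What SD does 0.60 imply?** If 0.60 is 1 point divided by an SD, the SD is 1/0.60 = 1.67 points. This is an inference, since 6.3 does not say that the 1% is the numerator. It also leaves two readings of 1.67:

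- (a) outcome SD: baseline-adjusted SD s = 1.67·√(1−r²)
- (b) SD of the pre-post change, with equal variances at both times: s = 1.67·√((1+r)/2)

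Reading (b) goes with a paired test. There r is taken only to 0.65, because beyond that the implied outcome SD, 1.67/√(2(1−r)), exceeds an assumed ceiling of 2.0.

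**3. ANCOVA power at 30 per arm.** Noncentrality = difference/(s·√(2/30)), df 57.

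| Difference | r | (a) outcome SD 1.67 | (b) change SD 1.67 |
|---|---|---|---|
| 1 point | 0 | 0.63 | 0.90 |
| 1 point | 0.5 | 0.75 | 0.75 |
| 1 point | 0.6 | 0.81 | 0.72 |
| 1 point | 0.65 | 0.85 | 0.71 |
| 0.3 points | 0 | 0.105 | 0.163 |
| 0.3 points | 0.5 | 0.124 | 0.124 |
| 0.3 points | 0.65 | 0.147 | 0.117 |
| 0.3 points | 0.8 | 0.208 | outside range |

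For 1 point, 0.80 is reached at r of about 0.58 or more under (a) but at r of about 0.33 or less under (b). The two readings move in opposite directions, and 6.3 does not allow a choice between them.

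For 0.3 points, the one-sided figures run from 0.17 to 0.31 under (a) and from 0.19 to 0.25 under (b).

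**4. If 0.3% means a pre-post change.** Paired test in one arm of 30: noncentrality (0.3/1.67)·√30 = 0.18·√30, df 29, power 0.16.

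**5. SD needed for 0.3 between arms.** The difference detectable with 80% power at 30 per arm is 0.736·s, so s must be at most 0.3/0.736 = 0.41 points.

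**6. Precision.** 95% CI half-width = t·SD·√(1−r²)·√(2/n), with t = 2.002 at df 57. For assumed SD 0.8 and r = 0.8: 2.002 × 0.8 × 0.6 × 0.258 = 0.25. For assumed SD 2.0 and r = 0: 2.002 × 2.0 × 1 × 0.258 = 1.03. With 20% dropout (24 per arm) the range is 0.28 to 1.16.

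**The case against.** **The protocol says plainly that this is not a confirmatory trial.** Section 6.3 disclaims testing and defers adequate power to a later trial, 9.4 says pilot, and 9.5 admits the limit. This stands: it makes 30 per arm defensible as a feasibility size and lowers the risk that a null result is misread. It does not repair the sentence that follows the disclaimer, which quotes a power and draws the sample size from it. Nor does any of this text mention the 0.3%.

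**The planned ANCOVA may have 0.80 power for 1 point anyway.** It may, as step 3 shows. A reader might infer that the trial is underpowered for its own effect size and needs 45 per arm, or that the ANCOVA works only with a correlation of 0.58 or more. Both inferences treat 0.60 as standardised by the outcome SD. With the change SD, which suits the paired wording, power for 1 point is 0.90 at r = 0 and the correlation condition reverses.

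**The 0.3% is a minimum, so 1% does not contradict it.** Agreed. The protocol's own review cites reductions of 0.32% for behaviour change, 0.7% for a text-message study and up to 1.0% for another. But a power figure at 1% says nothing about the minimum that the objective and hypothesis name.

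**The magnitudes rest on inference.** This also stands. The SD of 1.67, the correlations and the between-arm reading of 0.3% are not in the protocol. The low power for 0.3 points nevertheless holds on every reading of 6.3's ratio tried here, including the paired one.

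**Conclusion.** The mismatch is real: the only quantitative basis for 30 per arm is a power figure for another contrast and a larger effect. The 25 is not an arithmetic slip, and the source cited for it cannot be checked from the protocol.

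Conditional on an SD of 1.67, 30 per arm and no dropout, two-sided power for a 1-point between-arm difference is 0.63 (r = 0) to 0.81 (r = 0.6) if 1.67 is the outcome SD, and 0.90 (r = 0) to 0.71 (r = 0.65) if it is the change SD. A shortfall at 1 point is therefore not shown. Power for 0.3 points is about 0.1 to 0.2, at most 0.31 one-sided.

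The documents do not support calling the sample too small for a pilot or asking for more patients. Severity is minor to should-fix. Confidence is high in the textual mismatch and moderate in the magnitudes.

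**What to change.** Keep n=60 and the ANCOVA.

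- **Section 6.3:** delete the sentence on 25 per group and 0.80 power, and the *therefore*. Justify n=60 by feasibility and by the expected 95% CI half-width of the baseline-adjusted between-arm HbA1c difference at 12 weeks, using the sponsor's own SD, correlation and dropout, labelled as assumptions. The range of 0.25 to 1.03 points in step 6 is an illustration only and too wide to serve as the justification.
- **Alternative for 6.3:** if a power statement is kept, restate it for the two-arm ANCOVA with its difference, SD, correlation, sidedness and dropout.
- **Sections 3.5 and 5:** state whether the 0.3% is a between-arm difference. Add that the trial is not powered to confirm or exclude it, and that the difference will be reported with its 95% CI.

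The cost is protocol wording: no added patients and no change to the analysis. The downside is that the 0.80 disappears or becomes less favourable, and the sponsor must commit to an SD and a correlation.

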6.4 Sampling design

Nakuru county has 18 level 4 hospital(102). Purposive sampling will be used to select two hospitals, one in a rural setting, and another in an urban setting. Multistage random sampling with then be applied to randomly assign 15 participants in either the intervention or control arms using simple random sampling in each of the selected hospitals.

6.5 Recruitment

The officers-in-charge of the non-communicable disease clinics shall be enlisted to help in the recruitment of participants. The officers will receive the recruitment procedure guidelines prior to the onset of the study to ensure a standard approach in all the hospitals. During the clinic visits, the participants will be asked to participate in the study. Possible study participants will be given details on the study and asked to acknowledge their willingness to participate within 7 days. The recruitment is planned to take place between 15th July to 15th August 2021.

Due the COVID-19 disease the following precautionary measures shall be ensured by the research team, participants and hospital staff during recruitment, training and all activities in this study:

1. The study shall provide personal protective equipment (PPE) for all study participants and researchers.
2. Regular and thorough washing of hands with soap and water, or alcohol-based hand sanitizer provided by the research.
3. Maintaining a distance of at least 1 meter (5 feet) between yourself and anyone (who is coughing or sneezing), avoiding handshakes or hugging.
4. Persons with a cough or sneezing should stay home or keep a social distance but avoid mixing with others in a crowd.

5. Maintain good respiratory hygiene by covering your mouth and nose while coughing and sneezing with a handkerchief, tissue, or into flexed elbow.
6. Stay at home if you feel unwell with symptoms like fever, cough and difficulty in breathing.
7. All study participants should at all times wear a face mask to reduce the chances of transmission of the virus.
8. Any cases regarding the disease will be reported using the call line facility number 719. Correct messages to be relayed to the participants (if need be) will be received from *719#
9. Surfaces used during the research activities (e.g. desks, tables) and objects will be wiped with disinfectant regularly.
10. Surfaces used during the research activities (e.g. desks, tables) and objects will be wiped with a disinfectant regularly.

6.6 Randomization

We will apply simple random sampling through a computer-generated list of random numbers. The hospital diabetes registers from the two selected hospitals will be used to select patients on regular diabetes care from the hospital patient records. The patients will then be assigned numbers and randomly selected.

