7.4 Ethical issues

This study will be conducted in respect to the principles contained in the Declaration of Helsinki (111). A written informed consent will be obtained from all participants prior to their enrolment into the study (Appendix 1). The informed consent will allow the participant enough time to decide whether to be in the research study and to make that decision without any pressure from the researchers. Participants will also have the right to refuse to be in the study at all, and to stop participating at any time after study begins.

Study personnel shall ensure strategies to protect privacy interests relating to contact with potential participants, and access to private information at all times during the study. All study personnel shall sign and adhere to the Data Confidentiality Agreement for Study Staff (Appendix 6).

To ensure confidentiality, that an information disclosed by the participants shall not be divulged to others without permission in ways that are inconsistent with the understanding of the informed consent form. During consenting, subjects shall be informed of the precautions that will be taken to protect the confidentiality of the data and be informed of the parties who will or may have access.

The community engagement strategy shall ensure that the study will be conducted in a way that is respectful to individuals and communities to maximize social value. Additionally, internationally recognized standards of good practice with responsiveness to the local context (112) shall be adhered to.

The data from the study will be stored in a secure server where only authorized individuals will have access to the data. The parties will retain the data for 10 years after study completion, according to the General Data Protection Regulation (GDPR) (113). However, neither party will destroy information without first informing the other parties. In case of future testing, permission to conduct further studies shall be sort from the participants.

This study will seek the following approvals, permissions, and registration:

- Letter of support from Jomo Kenyatta University of Agriculture and Technology;
- Ethical approval from the African Medical Research Foundation-Ethics & Scientific Review Committee (AMREF-ESRC);
- Research permit from the National Council for Science Technology and Innovation (NACOSTI);
- Registration of clinical studies with human subjects that assess biomedical and/or health outcomes at clinicaltrials.gov (114).

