10.3 Schedule of activities

The study timelines are listed in Table 3 below

It is planned that the study will begin on 15 July 2021 to

Table 4. Schedule of Activities

	Wk 0	Wk 1	Wk 2	Wk 3	Wk 4	Wk 5	Wk 6	Wk 7	Wk 8	Wk 9	Wk 10	Wk 11	Wk 12	Wk 25
Planned Activity	23-Aug	30-Aug	06-Sep	13-Sep	20-Sep	27-Sep	04-Oct	11-Oct	18-Oct	25-Oct	01-Nov	08-Nov	15-Nov	14-Feb
Recruitment and allocation														
Baseline data collection														
Introduction call and text messages														
Intervention month 1														
Intervention month 2														
Intervention month 3														
Post-Intervention follow-up														

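### Section 6.6 (Randomization) describes only sampling from registers, and the protocol nowhere places arm assignment after consent and baseline or conceals it from recruiting staff

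*Protocol*

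**What the plan says.** Section 6.6 has three sentences. The method is: "We will apply simple random sampling through a computer-generated list of random numbers". The source is: "The hospital diabetes registers from the two selected hospitals will be used to select patients on regular diabetes care from the hospital patient records". The last step is: "The patients will then be assigned numbers and randomly selected". Arms, an allocation sequence, concealment and timing are not mentioned.

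Arms appear in section 6.4, which will "randomly assign 15 participants in either the intervention or control arms using simple random sampling in each of the selected hospitals".

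Section 6.5 describes entry by another route. Clinic officers help to recruit, and "During the clinic visits, the participants will be asked to participate in the study". Those approached are "asked to acknowledge their willingness to participate within 7 days". Section 7.3 has the hospital in-charges coordinate the identification of sampled respondents.

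On consent, section 7.4 says: "A written informed consent will be obtained from all participants prior to their enrolment into the study". It does not mention allocation.

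Table 4 in section 10.3 has a single row for "Recruitment and allocation", followed by a row for baseline data collection. Section 6.7 states that participants, care providers and the research team cannot be blinded.

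**The concern.** Sampling decides who is invited. Randomization decides which arm a consented person enters. Section 6.6 carries the second title but gives only the first procedure, and section 6.4 uses the vocabulary of sampling for assignment. A site team working from this text has no instruction on when the arm is drawn or who may know it.

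If the arm is known at invitation, three things can go wrong:

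- Clinic officers can invite selectively, and patients can accept or decline according to arm. The arms may then differ in willingness to act on advice, which section 9.6 names as the trial's main assumption.
- The interviewer-administered baseline tools, including self-perceived food literacy, can be answered with the arm known.
- People assigned but never consented contribute no data, so the intention-to-treat analysis in section 8.2 cannot include them.

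The ANCOVA in section 8.2 controls for baseline HbA1c. It does not remove differences in motivation.

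**Working it through.** The point is procedural, so most of the check consists of setting passages side by side. Two small calculations help.

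**1. Does 6.4 reproduce the planned sample?** Inputs: 2 hospitals and 15 participants (6.4), 2 arms, 60 in total with 30 per arm (6.3).

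- Reading 15 as per arm per hospital: 2 × 2 × 15 = 60, and 2 × 15 = 30 per arm. This matches 6.3.
- Reading 15 as per hospital in total: 2 × 15 = 30 overall. This does not match.

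So 6.4 intends a random assignment of 15 per arm in each hospital, that is, 15 of 30.

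**2. What does a draw of 15 of 30 require?** The list of 30 must be closed before the draw. Two lists could serve:

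| List used for the draw | What follows |
|---|---|
| 30 consented participants with baseline done | Arm unknown at invitation, consent and baseline; exact balance |
| 30 names sampled from the register | Arm can be known before approach; each refusal leaves a gap in one arm, with no stated rule for filling it |

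The protocol does not say which list is meant. The word participants in 6.4 does not settle it, because 6.5 uses the same word for people who have not yet been asked.

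**3. Do the dates allow the sound version?** Inputs: recruitment runs to 15 August with 7 days to reply (6.5); Week 0 is dated 23 August (Table 4).

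- Last reply: 15 + 7 = 22 August, one day before Week 0.

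A consented list can therefore be complete before Week 0. However, Table 4 starts on 23 August and still has a recruitment row, so the dates do not confirm that this is the plan.

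**4. Is allocation tied to consent or baseline anywhere?**

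| Place | What it fixes | What it leaves open |
|---|---|---|
| 6.4 | 15 per arm per hospital | Timing, concealment |
| 6.5 | Approach at clinic, 7 days to reply | Whether the arm is already drawn; link to the register sample in 6.6 |
| 6.6 | Random selection from registers | Assignment altogether |
| 6.7 | No blinding of three groups | Concealment before enrolment |
| 7.3 | In-charges coordinate identification of sampled respondents | Whether they see arms |
| 7.4 | Consent before enrolment | Order of consent and allocation |
| Table 4 | Allocation joined with recruitment, listed above baseline | Actual weeks (cell markings not legible) |

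No row supplies the order of consent, baseline and allocation, or any concealment.

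**The case against.** The strongest reply is that sections 6.6, 7.4 and 6.4 can be read in sequence: sample from the register, obtain consent, then assign. The dates permit a batch draw of 15 of 30 consented people in each hospital, which would be valid and exactly balanced. Figure 3, said to show the workflow, is not visible, and section 6.5 mentions separate recruitment guidance for the officers. The primary outcome is a laboratory assay, tested outside the hospitals, with requisitions carrying an identification code. Arm-aware baseline questionnaires would therefore touch secondary outcomes rather than the HbA1c measurement.

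Much of this stands, and it rules out stronger readings that a reader might infer:

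- That the trial has no random allocation. Section 6.4 provides for it.
- That the register draw fixes the arm before a patient is approached. Section 6.6 mentions no arm, so it fixes none.
- That Table 4 proves allocation precedes baseline. Only row order survives, and recruitment and allocation share one row.
- That drawing 15 of 30 is incompatible with clinic recruitment. The dates leave room for it.
- That a baseline HbA1c imbalance would carry through in full to the treatment effect. The planned ANCOVA largely removes that component.

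The reply does not close the gap. The sound sequence is one available reading, and no visible passage requires it. Laboratory measurement protects the assay, not the choice of who enters each arm. The order and concealment of allocation also belong to trial conduct, so a separate statistical analysis plan would not be expected to supply them.

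**Conclusion.** The point holds in this form: the section headed Randomization states a sampling rule, the one assignment sentence reuses sampling language, and no visible passage places assignment after consent and baseline or hides it from recruiting staff. With participants, care providers and the research team unblinded, the protocol permits selection by arm. It does not prescribe it.

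The gap covers the entry of all 60 participants and bears on the validity of the primary comparison. No numerical size is given, because refusal by arm and its link to motivation or outcome are not in the documents. The conclusion assumes that neither Figure 3 nor the recruitment guidance states the order and the concealment; if either does, the remaining task is to bring 6.4, 6.6 and Table 4 into line with it. The change should be made before recruitment opens, because selection at entry cannot be repaired afterwards.

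**What to change.** - **6.6, sampling:** say that the register draw decides only whom to invite, and reconcile it with the clinic-visit approach in 6.5.
- **6.4 and 6.6, allocation:** state that, after written consent and completed baseline measurements, participants are allocated 1:1 within each hospital from a computer-generated sequence concealed from recruiting staff and enumerators. Either a batch draw of 15 of the 30 consented per hospital or a restricted list would do. The batch draw keeps the numbers already in 6.4. Stop using simple random sampling as the name of the allocation rule.
- **Table 4:** separate allocation from recruitment and list it after baseline data collection. Check Figure 3 against the same order.

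The cost is rewording three places and a short script for the sequence. The small downside is that an existing team member outside recruitment must hold the sequence. No patients or visits are added.
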